4.12.7 Subject Discomfort with Study Drug

The occurrence and severity of menstrual pain or cramping will be summarized by cycle for the ECYC population for the first year of treatment.

Only cycles with assessment of bleeding (menstruation) will be included in the analysis.

The analysis will be repeated by parity status at enrollment.

Experience of any menstrual pain or cramping will be recorded daily by the subject in the e-diary in the first year. If menstruation reported is in a cycle, but menstrual pain or cramping is completely missing, then missing values will be imputed as pain or cramping of the maximum intensity.

The following parameters will be reported in the table and data will be presented in the listing:

- Number (%) of subjects with menstrual pain by cycle
- Number (%) of subjects with menstrual pain by maximum severity by cycle
- Number (%) of subjects with menstrual cramping by cycle
- Number (%) of subjects with menstrual cramping by maximum severity by cycle

4.12.8 Cumulative VeraCept Continuation Rates

Cumulative VeraCept continuation rates for Years 1 through 5 will be estimated via Kaplan-Meier method for the Safety population. The complementary log-log transformation will be used to construct 95% CIs. The number and percentage of subjects with each reason for discontinuation will be summarized. The analysis will also by repeated by parity at enrollment.

Time to VeraCept discontinuation from successful insertion will be analysis variable.

- If a subject discontinued VeraCept because of desire of pregnancy, the subject will be censored at the cycle of removal.
- If a subject discontinued because of pregnancy, VeraCept should be removed. However, according to protocol, the study drug could be removed at the time of delivery. So, for consistency, the subject will be censored at the cycle of removal or conception if not removed.
- If a subject is lost to follow-up, she will be censored at the last cycle in which the study drug was known to be in place.
- If a subject completed the exposure period, the subject will also be censored at the cycle of the period end.

4.12.9 VeraCept Expulsion Rates

Cumulative VeraCept Expulsion Rates for Years 1 through 5 will be estimated via Kaplan-Meier method for the Safety population. The complementary log-log transformation will be used to construct 95% CIs. The subgroup analysis will also be repeated by parity status at enrollment.

VeraCept expulsion includes both total expulsion and partial expulsion. Total expulsion is defined as cases in which VeraCept is observed in the vagina, not shown in the uterus by ultrasound, or if the women confirmed expulsion. Partial expulsion cases are defined as when VeraCept is visible in the cervical canal by gynecologic exam or ultrasound. If partially expelled VeraCept is removed, the removal will be considered an expulsion event for this analysis.

- Time to expulsion in cycles will be defined as time to total expulsion discovered or removal of the partially expelled VeraCept from the date of successful insertion
- Removal of VeraCept for any other reason will be censored at the removal cycle.
- If a subject discontinued because of pregnancy, the subject will be censored at the cycle of conception
- Lost-to-follow-up will be censored at the last cycle where VeraCept is in Situ.
- Those with VeraCept still in place for protection at the end of exposure period will be censored at the end of exposure period.

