| Once you have purchase on the stem of the device with the second forceps, apply gentle traction to remove VeraCept. If it becomes necessary to pass the narrow forceps through the internal os, strongly consider placing a cervical block (anesthesia). This will require use of a tenaculum and possibly dilation of the cervical canal and/or ultrasound guidance. If VeraCept cannot be removed using the above techniques, consider use of hysteroscopy. Contact the Sebela national PI for consultation: If you have concern regarding embedment If you would like consultation regarding a challenging removal If you have reason to believe that the device will not be able to be retrieved with a hysteroscope. After removal of VeraCept, examine the device to ensure that it |
| is intact* |
| Determine the location of VeraCept by ultrasound. |
| If the device is not visualized in the uterine cavity, obtain a KUB radiograph or CT to evaluate if the device is in the abdominal cavity. If it is suspected that the study device has been translocated into the abdominal cavity, manage appropriately and immediately notify the Sebela national PI. If the device is not visualized radiographically, it is presumed to have expelled |
| |

| Removal Situation(s) | Instructions |
|---|--|
| | Initially, attempt to grasp the strings within the cervical canal. If the position of the device within the uterus requires that you pass the instrument into the uterine cavity, it is recommended that you place a cervical block and use a tenaculum. Consider use of dilation of the cervical canal and ultrasound guidance as needed. If VeraCept cannot be removed using the above techniques, consider use of hysteroscopy. |
| *After removal of VeraCept, examine the device to ensure that it is intact. | If the device does not appear to be intact or if any defects are discovered (e.g., broken strings, device broke upon removal): Retain the device Notify the medical monitor immediately to determine if further assessment or analysis is needed |

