4.1.5 Exposure Periods

The first exposure cycle starts on Day 1 of successful study drug insertion. A full exposure cycle is comprised of 28 days. One woman-year comprises thirteen 28-day cycles. The following exposure periods are defined for analysis in terms of planned study days and study cycles to facilitate the efficacy and certain safety analyses.

Exposure Period	Study Day of Period Start (PSTDY)	Study Day of Period End (PENDY)
Year 1 (Cycle 1- Cycle 13)	1	364
Year 2 (Cycle 14-Cycle 26)	365	728
Year 3 (Cycle 27-Cycle 39)	729	1092
Year 4 (Cycle 40-Cycle 52)	1093	1456
Year 5 (Cycle 53-Cycle 65)	1457	1820
First 2 Years (Cycle 1-Cycle 26)	1	728
First 3 Years (Cycle 1-Cycle 39)	1	1092
First 4 Years (Cycle 1-Cycle 52)	1	1456
5 Years (Cycle 1-Cycle 65)	1	1820

Type of Events and Study Day During an Exposure Period

ЕТҮРЕ	Event	Study Day of Event (EVTDY)		
A	Expulsion	Study Day of Expulsion date		
В	Expulsion followed by conception within 7 days	Study Day of Expulsion date		
С	Removal	Study Day of Removal date		
D	Removal followed by conception within 7 days	Study Day of Removal date		
Е	Pregnancy before expulsion	Study Day of Conception date		
F	Pregnancy before removal	Study Day of Conception date		
Н	Lost to follow-up without pregnancy, expulsion or removal	Study Day of Last Date Device in Situ.		
I	Complete period without pregnancy, expulsion or removal	Study Day of Period End Date		

Note: Removal due to partial expulsion will be treated as expulsion

Exposure Duration in Days (EXDUR):

if EVTDY-PSTDY>0 then EXDUR = min(EVTDY-PSTDY+1, PENDY-PSTDY+1); else EXDUR=.;

Exposure Duration in Cycles (NCYCF) = EXDUR/28

Number of Completed Cycles (NCYCC) = INT(NCYCF)

Number Relevant Cycles (NCYCR)

- =NCYCC+1 if last partial cycle is >=23 days
- =NCYCC+1 if last partial cycle ETYPE is B or D or E or F
- =NCYCC, otherwise.

Number of Cycles with back-up contraceptives (including emergency contraception) or no intercourse within the period or there is no diary data (NCYCEXCL):

Exclude from NCYCEXCL the cycle in which the subject had an on-treatment pregnancy (ETYPE is B, D, E, F).

Back-up contraceptives or intercourse history are recorded in subject's diary.

If there are missing values then they will be handled as follows:

Missing back-up contraceptive diary entries will be treated as no back-up contraceptive use.

Missing intercourse diary will be treated as no intercourse.

Number of Evaluable Cycles (NCYCEV) = NCYCR-NCYCEXCL

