4.1.8 Study Drug Expulsion Rate

The expulsion rate is defined as cumulative probability of device expulsion at the end of an exposure period. It is calculated as failure probability from a survival analysis.

Time variable

CYCLEN= Time to expulsion in cycles (uncompressed)

Event variable Expulsion

If ETYPE is A or B, then EXPULSION=1; else EXPULSION=0

Expulsion includes removal due to partial expulsion

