4.1.9 Continuation Rate

Continuation rate is defined as the cumulative probability of study drug use at the end of a study period. It is calculated as survival probability from a survival analysis.

Time variable:

CYCLEN= Time to study drug discontinuation in cycles (uncompressed)

Event Variable DISCONTINUATION:

If ETYPE is A or B or C or D then DISCONTINUATION=1;

else DISCONTINUATION=0

Those lost to follow-up and became pregnant before removal or expulsion are censored.

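### SAP 4.12.9 counts a device that has perforated the uterus as a total expulsion, because absence from the uterus on ultrasound is enough on its own

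*SAP*

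**What the plan says.** **Definition.** SAP 4.12.9 gives three alternative criteria for a total expulsion: "Total expulsion is defined as cases in which VeraCept is observed in the vagina, not shown in the uterus by ultrasound", or confirmed by the woman. The event is timed at discovery. A later bullet in the same section adds: "Removal of VeraCept for any other reason will be censored at the removal cycle".

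**Coding.** SAP 4.1.5 assigns each woman an event type (ETYPE). Its only rule linking removal to expulsion is "Note: Removal due to partial expulsion will be treated as expulsion". SAP 4.1.8 then sets "If ETYPE is A or B, then EXPULSION=1; else EXPULSION=0", and SAP 4.1.9 sets "If ETYPE is A or B or C or D then DISCONTINUATION=1".

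**Clinical instruction.** Protocol Appendix 5 treats the same ultrasound finding as undecided: "If the device is not visualized in the uterine cavity, obtain a KUB radiograph or CT". It continues: "If it is suspected that the study device has been translocated into the abdominal cavity, manage appropriately". A device is taken as expelled only if that imaging does not show it.

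**Endpoints.** Protocol 5.2 and SAP 2.2 list uterine perforations and expulsion rates as separate safety endpoints. Protocol 6.2 includes perforation among events reported in under 2% of pooled subjects, and notes that surgery may be needed to retrieve the device from the peritoneal cavity.

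**The concern.** An empty uterus on ultrasound has two explanations: the device has left through the cervix, or it has gone through the uterine wall. The first is an expulsion. The second is a perforation, a different harm with different management. The SAP definition does not separate them; Appendix 5 does.

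At stake is what the expulsion rate means. A woman whose device is retrieved from the abdomen would appear in the perforation table, correctly, and also as an event in the cumulative expulsion curve, where she does not belong. The stated rule therefore gives a wrong classification; this is more than missing detail.

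**Working it through.** The plan states no expected expulsion or perforation rate, so there is no figure to reproduce. The check traces one case through the rules and then sizes it.

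**1. One case through the rules.** Take a device found in the abdomen after ultrasound showed an empty uterus, with no pregnancy.

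| Rule | As written | With the fix below |
|---|---|---|
| 4.12.9 | meets the ultrasound criterion: total expulsion at discovery | excepted |
| ETYPE (4.1.5) | A | C, dated at discovery |
| EXPULSION (4.1.8) | 1 | 0, censored at discovery |
| DISCONTINUATION (4.1.9) | 1 | 1 |
| Perforation, as an event of special interest (4.12.2) | reported | reported |

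Only the expulsion rate changes. If she conceives within the 4.1.6 window, her code is B, D, E or F; each gives PREGNANCY = 1, and the fix keeps that definition.

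**2. Crude size.** With 1,605 enrolled (protocol 20.9), one case is 1/1,605 = 0.062 percentage points. The expulsion analysis uses the Safety population. Assuming the Phase 2 placement success of 283/286 (protocol 1.1.3), that is 1,605 × 283/286 ≈ 1,588 women, and 1/1,588 = 0.063 points. For assumed counts of 5 and 10 cases on 1,605, the excess is 0.31 and 0.62 points.

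**3. Kaplan-Meier size.** Let n be the number at risk and S(t−) the expulsion-free proportion just before the case. Scored as an event, the curve drops to S(t−)(1 − 1/n); scored as a censoring, it stays at S(t−). The difference is S(t−)/n, at most 1/n. Using the expected minimum numbers in protocol 20.9:

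| Time | n | Limit 1/n | With S = 0.95 (assumed) |
|---|---|---|---|
| End of Year 3 | 620 | 0.161 points | 0.153 |
| End of Year 5 | 350 | 0.286 points | 0.271 |
| End of Year 8 | 200 | 0.500 points | 0.475 |

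The 620 and 350 count only women up to age 35, and 200 covers all ages. All are stated as minimums, so the limits are on the high side. Year 8 is in protocol version 7.0; the SAP stops at Year 5.

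**4. Ceiling on the count.** If the under-2% listing in protocol 6.2 held here, 2% × 1,605 = 32.1, so at most 32 women, or 32/1,605 = 1.99 points crude. This is an outer limit, not an estimate. The 2% is a listing threshold for pooled studies, and not every perforation leaves the uterus empty on ultrasound.

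**The case against.** **Counting any loss from the uterus is conservative.** It makes expulsion look worse, and perforation is tabulated whatever ETYPE is assigned. Both points are right and limit the severity. They do not make a perforation an expulsion when the two are separate endpoints.

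**The mismatch is a matter of versions.** The SAP follows protocol version 3.0; the revision history places the removal instructions in version 6.0, and protocol section 20 has the SAP finalized before database lock. That explains the gap, but 4.12.9 still needs the change. The SAP must in any case be extended to Years 6 to 8.

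**Safeguards exist.** These are the central ultrasound reader (protocol 4.5), Medical Monitor review of both events, and the exit visit, which refers to Appendix 5 for removal. They help recognise a perforation. None alters the definition that drives EXPULSION.

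**A code may be missing from our copy.** The event table as read from the PDF skips the letter G. No weight is placed on that, since the point rests on the 4.12.9 definition.

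**Stronger readings that a reader might infer.** One is that the SAP gives three conflicting answers for such a case: expulsion at discovery, censoring at surgical removal, or no event if the device stays where it is. The text does not support this. Section 4.12.9 holds the only definition of expulsion and dates it at discovery, and its censoring bullet covers removal for reasons other than those already defined as expulsion. Another is that a woman whose translocated device is not removed would stay a continuing user. That is weak too. Type H is "Lost to follow-up without pregnancy, expulsion or removal", type I also requires a period free of expulsion, and the last bullet of 4.12.9 limits end-of-period censoring to devices still in place and protecting.

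**Conclusion.** The point stands as a minor one. Read as written, SAP 4.12.9 has one answer for a translocated device, and it is the wrong one: an expulsion event at discovery, in addition to the perforation.

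The excess is about 0.06 percentage points crude per case, and at most 0.16 points at Year 3 or 0.29 at Year 5 in the Kaplan-Meier estimate. These sizes rest on the plan's expected numbers. The number of such cases cannot be derived from the documents.

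The endpoint is descriptive and the error overstates expulsion. Nothing here shows that perforations go unreported, that the continuation rate is wrong, or that the primary Pearl Index is affected.

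**What to change.** **SAP 4.12.9.** After the ultrasound criterion add: *unless the device is located outside the uterine cavity by radiograph, CT or surgery*. State that this means beyond the uterine wall, so that devices in the cervical canal or vagina stay expulsions.

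**SAP 4.1.5.** Add a note to the event table: *A device found outside the uterine cavity is treated as a removal dated at discovery (ETYPE C, or D, E or F if the 4.1.6 pregnancy definition is met).* Without a pregnancy this gives EXPULSION = 0, censored at discovery, and DISCONTINUATION = 1. Sections 4.1.8 and 4.1.9 need no change.

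**Cases without radiograph or CT.** Devices absent on ultrasound and not located elsewhere remain expulsions under this wording. List those with no radiograph or CT as *presumed, location unconfirmed*.

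**Protocol 4.5 and 12.11, for patient safety.** Both go from ultrasound to study exit without mentioning further imaging. Add a cross-reference to the Appendix 5 imaging step for non-pregnant women whose device is not seen on ultrasound and was not recovered or seen to pass.

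**Cost.** One clause with its clarification and one table note in the SAP, a line in the listing, and one sentence in each of two protocol sections. A few women have imaging that Appendix 5 already specifies. The perforation count may rise slightly if that imaging finds devices otherwise presumed expelled.

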11 STUDY SCHEDULE OF ASSESSMENTS

A schedule of assessments for all VeraCept subjects is provided in Table 1.

Table 1: Study Schedule of Assessments

| | | Screen | | | Years 1-8 | | | 0 | ther |
|---|---|-----------|--|---|---|--|--------------------------------|---|---|
| | | Screening | Enrollment (VeraCept Placement) Day 1 | Office Visits: W 6 ± 1 w W 13 ± 1w W 26 ± 2w W 52 ± 2w | Regular Contact ⁹ : W 17, 21, 30, 34, 39, 43, 47 ±1w Monthly M13- 17, M19-23, M25-29, M31-35 (±1 w) | Office Visits: M 18, 24, 30, 36, 42, 48, 54, 60, 66, 72, 78, 84, 90 (± 1 m) | M 96 + 1 m or Exit Visit | Contact to confirm pregnancy for those desiring pregnancy ⁸ | 30-Day Post- Removal AE follow-up |
| | Assessment of Eligibility | X | X | | | | | | |
| / tics | Distribution of subject materials, if applicable | X | | | | | | | |
| Initiation/ Subject Characteristics | Informed consent and assent, if applicable, PHI and Bill of Rights forms (where applicable) | X | | | | | | | |
| Init Su sara | Demographics and baseline characteristics | X | | | | | | | |
| C | Med/surgical, gynecological and menstrual history | X | | | | | | | |
| | Vital signs and weight | X | X | X | | X | X | | |
| | Height | X | | | | | | | |
| | General physical exam | X | | | | | X | | |
| od v | Pelvic exam (string check if post IUS insertion) | X | X^1 | X^1 | | X^1 | X^1 | | |
| Safety and Efficacy | Cervical cytology | X | | | | | | | |
| ıfet | Cervical infection tests | $X^{5,7}$ | | | | | | | |
| SS | Transvaginal ultrasound ² | | X^2 | X^2 | | X^2 | X^2 | | |
| | Pregnancy test-urine | X | X | X | | X | X^4 | | |
| | Prior and concurrent medication | X | X | X | X | X | X | | |
| | Adverse events | | X | X | X | X | X | | X^{16} |
| | Contact IWRS | X^{12} | X^{13} | | | | X | | |
| | IUD placement | | X | | | | | | |
| | IUD placement ease | | X | | | | | | |
| | IUD placement pain (11-point scale) | | X^{10} | | | | 7 714 15 | | |
| ı | IUD removal | | | | | | X ^{14,15} | | |
| Other | IUD removal ease | | | | | | X X ¹¹ | | |
| 0 | IUD removal pain (11-point scale) Concomitant contraception | | X | X | X | X | X ¹⁴ | | |
| | Subject education - need for contraception | X | X | X | X | X | X | | |
| | Subject education - need for contraception Subject e-Diary training and re-training | X^{3a} | X | X | X | X | Λ | | |
| | e-Diary reviewed with subject ⁶ | Λ | X^{3a} | X^{3b} | X ^{3b} | X^{3b} | X^{3b} | | |
| | Discontinued Subject Desiring Pregnancy | | 21 | 71 | 21 | 21 | | X8 | |

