- 9. Contact subject (e.g., via phone, email, etc.). Starting at Week 17 from day of VeraCept insertion.
- 10. See Appendix 2 for the IUD Insertion Subject Numeric Pain Rating Scale
- 11. See Appendix 3 for the IUD Removal Subject Numeric Pain Rating Scale
- 12. Upon receipt of informed consent and assent, if applicable, contact the IWRS to register the subject, initiate the subject's screening diary and obtain a subject number
- 13. Contact the IWRS prior to insertion to obtain an enrollment number, the IUS dispensation assignment, and initiate the enrollment diary. If an IUS insertion is a failure, contact the IWRS to record the IUS insertion failure and to obtain a second IUS dispensation assignment or to discontinue the subject
- 14. See Appendix 4 for Pre-Removal Planning Timing
- 15. See Appendix 5 for Removal Instructions
- 16. An additional contact will be performed 30 days post-removal or expulsion for any AEs that were ongoing at the time of VeraCept removal. If the date of expulsion is unknown the additional contact will be performed 30 days after the date of expulsion discovery.
- 17. Subjects completing at least 6 years (72 months) of study will complete a Subject Satisfaction Survey at the Exit Visit.

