4.1.4 Analysis Windows

For analysis purpose, early termination visits and unscheduled follow-up visits will be assigned analysis visits according to the analysis windows in the following table. This mapping applies to labs, vital signs, and all other data planned to be collected and analyzed by visit in the SDTM finding domains. Where multiple measurements for a particular parameter appear within an analysis window the result closest to target day will be used. If equidistant, the later result will be used for the summary measure. Though all measures may not be used in the data summaries (e.g., 2 lab measures within the same analysis visit window), all measurements appear in the datasets and listings.

Analysis windows:

		Analyzia	Analysis Window			
Scheduled Visit	Analysis	Analysis Window	Lower	Upper		
(Subject Visit Window)	Visit	Target Day	Bound	Bound		
Visit 1/Screening						
Visit 2 (Day 1)	Baseline	1		1		
Visit 3 (Week 6±1 week)	Week 6	42	2	67		
Visit 4 (Week 13±2 weeks)	Week 13	91	68	137		
Visit 5 (Week 26±2 weeks)	Week 26	182	138	273		
Visit 6 (Week 52±2 weeks)	Week 52	364	274	456		
Visit 8 (Month 18± 1 month)	Month 18	548	457	639		
Visit 9 (Month 24± 1 month)	Month 24	730	640	822		
Visit 10 (Month 30± 1 month)	Month 30	913	823	1004		
Visit 12 (Month 36± 1 month)	Month 36	1095	1005	1187		
Visit 13 (Month 42± 1 month)	Month 42	1278	1188	1369		
Visit 14 (Month 48± 1 month)	Month 48	1460	1370	1551		
Visit 15 (Month 54± 1 month)	Month 54	1643	1552	1734		
Visit 16 (Month 60± 1 month)	Month 60	1825	1735	≥1735		

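### The SAP gives expulsions two different dates, and under the discovery-date rule unnoticed expulsions found at an anniversary visit after the 364-day year has closed drop out of that year's cumulative Kaplan-Meier rate

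*SAP*

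**What the plan says.** Cumulative expulsion rates are a secondary safety endpoint, estimated by Kaplan-Meier (Protocol 5.2 and 20.7.3 through Year 8; SAP 4.12.9 through Year 5).

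- **Event date.** SAP 4.12.9: "Time to expulsion in cycles will be defined as time to total expulsion discovered or removal of the partially expelled VeraCept". The event table in SAP 4.1.5, which feeds the time variable CYCLEN used in SAP 4.1.8, gives "Study Day of Expulsion date" for codes A and B.
- **The two dates can differ.** Protocol Table 1, footnote 16: "If the date of expulsion is unknown the additional contact will be performed 30 days after the date of expulsion discovery". The SAP has no rule for an unknown expulsion date in this analysis.
- **Years.** SAP 4.1.5: "A full exposure cycle is comprised of 28 days" and "One woman-year comprises thirteen 28-day cycles". The periods end on Days 364, 728, 1092, 1456 and 1820.
- **Visits.** SAP 4.1.4 sets targets at Days 364, 730, 1095, 1460 and 1825, with windows of 2 weeks (Week 52) or 1 month (later visits) on either side. In Protocol Table 1 the last visit is "M 96 + 1 m or Exit Visit", a one-sided window.
- **Detection.** Women need not check strings routinely (Protocol 4.5), and ultrasound is done only if clinically indicated. A partial expulsion is defined by examination or ultrasound (SAP 4.12.9).

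**The concern.** An expulsion the woman does not notice is found at the next office visit with a string check. If it is dated at that visit, it is dated late. From Month 24 on, an on-target anniversary visit falls a few days after the analysis year has closed, so the expulsion misses the landmark it belongs to. Late dating can only move an event to a later time, so each cumulative landmark is either right or too low. The landmarks include Year 3, which supports the submission (SAP 4.4). At the last reported landmark there is no later one to pick up the event. The two date rules also let two programmers produce different rates from the same data.

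**Working it through.** **1. Reproduce the plan's days.** Year end = 13 × 28 × k gives 364, 728, 1092, 1456 and 1820, as in SAP 4.1.5. Visit target = months × 365/12, rounded, gives 730, 1095, 1460 and 1825, as in SAP 4.1.4. Week 52 is Day 364.

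**2. Cycle of an on-target finding, CEIL(day/28).**

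| Visit | Target day | Cycle | Last cycle of the year |
|---|---|---|---|
| Week 52 | 364 | 13 | 13 |
| Month 24 | 730 | 27 | 26 |
| Month 36 | 1095 | 40 | 39 |
| Month 48 | 1460 | 53 | 52 |
| Month 60 | 1825 | 66 | 65 |

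A Week 52 visit on target stays in Year 1. The other four fall in the first cycle of the next year.

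**3. Share of window days after the year end** (1 month taken as 30 days). Week 52: 14/29 = 48%. Month 36: 33/61 = 54%. Over Months 24 to 60 the share runs from 52% to 57%.

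**4. Share of a year's unnoticed expulsions found after its end** (onset uniform within the year). Only those after the mid-year check can move.

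- Visits on target, Year 3 (Month 30 check on Day 913): (1092 − 913)/364 = 49%. Years 2 to 5 give 49%; Year 1 gives 0%.
- Visits uniform over the window, Year 3: 0.541 × 0.492 = 0.266 for late anniversary visits. Add 0.017 for expulsions between an early visit and the year end, and the total is about 28%. The same steps give about 25% for Year 1.

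**5. Coding at the period end.** SAP 4.1.5 caps exposure at the period end. If an expulsion discovered on Day 1825 keeps code A in the 5-year period, exposure = min(1825, 1820) = 1820, cycle 65, counted as an event. If the woman is coded I (period completed), she is censored. The event table is titled for events during an exposure period, which favours code I. Applied generally, code A with the cap would also pull a Year 5 expulsion into cycle 39 of the 3-year analysis, which cannot be meant. The SAP does not settle it.

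**6. Year 8, by extension.** With 13-cycle years, Year 8 would end on Day 104 × 28 = 2912. Month 96 is Day 2920, with a window to about Day 2950, so every in-window visit would fall after the year end (cycle 105 or later). Share of Year 8 unnoticed expulsions affected: (2912 − 2738)/364 = 48%, where 2738 is the Month 90 target.

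**7. Size.** Assumed, because the documents give neither: expulsion of 3% in Year 1, 1% in each of Years 2 and 3, and 0.7% a year later; 25-75% found only at visits. Shortfall ≈ that year's rate × unnoticed share × share moved.

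| Landmark | Visits over the window | Visits on target |
|---|---|---|
| Year 1 | 3 × (0.25 to 0.75) × 0.25 = 0.19 to 0.56 points | 0 |
| Year 3 | 1 × (0.25 to 0.75) × 0.28 = 0.07 to 0.21 points | 1 × (0.25 to 0.75) × 0.49 = 0.12 to 0.37 points |
| Year 8 | 0.7 × (0.25 to 0.75) × 0.48 = 0.08 to 0.25 points | the same |

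**The case against.** Much can be said for leaving this alone, and several stronger readings do not survive.

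- **A reader might infer that late-found expulsions are never counted.** They are: each is recorded as an adverse event (Protocol 12.11), summarised as an event of special interest, and tabulated among reasons for discontinuation. What is at risk is the Kaplan-Meier rate only, and even there the cap may retain the event.
- **A reader might infer that every yearly rate is too low.** That fails for a Week 52 visit on Day 364 and for visits early in the two-sided windows. It also fails for single-year increments, which gain events carried over from the year before. Only cumulative rates are biased in one direction.
- **A reader might take Day 2912 as the SAP's boundary.** The SAP is written to protocol version 3.0 and stops at Day 1820. The Month 96 result holds only if 13-cycle years are carried forward.
- **The unnoticed share may be small.** The daily diary asks about expulsion (Protocol 13), and monthly contacts run to Month 35. The Year 1 figure also needs flat risk within the year. If risk is concentrated early, the checks at Weeks 6, 13 and 26 would shrink it.

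All of this stands as a limit on size and wording. It does not remove the conflict between the two date rules, the missing rule for an unknown date, or the day arithmetic.

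**Conclusion.** The point holds in limited form. The SAP dates the same event in two ways. Under the discovery rule, unnoticed expulsions after the mid-year check are left out of that year's cumulative Kaplan-Meier rate when the anniversary visit falls after the year end. That is about half of in-window visits, and all on-target visits from Month 24. At the final landmark they may be lost from that rate, depending on a code the SAP leaves open.

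The effect is downward and modest: roughly 0.1 to 0.2 percentage points at Years 3 and 8 with visits spread over their windows, and up to about 0.4 at Year 3 if visits cluster on target. Year 1 ranges from nothing to about 0.6 points, depending on visit timing. These sizes rest on the assumed rates and unnoticed share; the dating conflict and the day counts come from the documents. The endpoint is descriptive, with no test or threshold attached. The change is still worth making because it affects a reported safety rate and costs little.

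**What to change.** For the expulsion-rate analysis only:

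1. Use one date rule in SAP 4.12.9 and for codes A and B in 4.1.5: the known expulsion date or, only if it is unknown, the midpoint between the last examination confirming the device in place and discovery. For example, a Month 36 finding (Day 1095) after a Month 30 check (Day 913) is dated Day 1004, cycle 36, Year 3.
2. Assign the event to the year containing that date. State that an expulsion so dated within a period is code A or B even if discovered after the period end.
3. Use findings through the Month 60 or Month 96 exit examination for the final landmark, and define Years 6 to 8 when the SAP is brought up to the current protocol.
4. Do not move an event whose known date is after the year end. A known Day 735 expulsion stays in Year 3.
5. Do not use the imputed date for the 7-day on-treatment pregnancy window in SAP 4.1.6, where it could reclassify pregnancies.

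The cost is a few sentences, minor programming and slightly higher reported expulsion rates.
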